2.3.2 Phase I

The primary objective of the phase I part of the study is to determine the maximum tolerated dose (MTD) of lenalidomide when given in combination with obinutuzumab for subsequent testing in the phase II part of the trial.

There are three predefined dose levels for lenalidomide (10 mg, 15 mg, 20 mg) with a fixed dose of obinutuzumab (1000 mg) as outlined in Table 1.

Dose limiting toxicity (DLT) will be assessed during the first course of each cohort (28 days), and refers to a medically significant event which meets one of the following criteria using National Cancer Institute Common Terminology Criteria for Adverse Events (NCI CTCAE) version 4:

- Grade 3 or higher non-hematologic AE which is felt to be related to the study drug by the investigator with the exception of the following:
 - Transient grade 3 or less infusion reaction that completely resolves within 24 hours.
- Grade 4 hematologic toxicity (Platelet count is defined as <25,000 for the purposes of determining DLT).
- Grade 3 neutropenia with elevated temperature (defined as >= 101 degrees F to be confirmed on two occasions).
- Grade 3 thrombocytopenia with bleeding.
- Treatment delay of greater than 2 weeks due to treatment related toxicity.

Prior to advancing/changing dose levels a cohort summary will be completed and submitted to the Clinical Research Monitor in the IND Office.

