HTLV testing is required in patients from endemic countries (Japan, countries in the Caribbean basin, South America, Central America, sub-Saharan Africa, and Melanesia)

- Pregnant or lactating
- ECOG performance status greater than 2.
- Participation in another clinical trial with drug intervention within 21 days prior to start of Cycle 1 and during the study
- Patients with SLL/CLL will be excluded during the phase I portion of the study

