4. TREATMENT PLAN

4.1 Phase I

Three dose levels of lenalidomide (10 mg, 15 mg, 20 mg) will be evaluated with a fixed dose of obinutuzumab (1000mg) as outlined in Table 1. (obinutuzumab will be given in divided doses on cycle 1; 100mg IV on day 1, and 900mg IV on day 2, subsequent doses will be given over 1 day) Up to 18 patients may participate in the Phase I component of the study, depending on the level at which toxicity is observed. Subjects will be assigned to a dose level based on the order of study entry and toxicities seen in prior patients. The dose escalation process is described below. There will be no intra-patient dose escalation. DLT will be assessed during the first course of each cohort (28 days), and refers to a medically significant event which meets criteria using National Cancer Institute Common Terminology Criteria for Adverse Events (NCI CTCAE) version 4. (see section 2.3.2)

Table 1. Dose levels to be tested in phase I portion

Dose Level	Lenalidomide Dose (days 2-22 followed by 6 days of no therapy)	Obinutuzumab dose
-1	5 mg	1000mg IV
1	10 mg	
2	15 mg	
3	20 mg	

4. 2 Phase II

Additional pts will be enrolled into two cohorts at the recommended dose level (MTD) established in Phase I up to a maximum of 30 patients each in two independently enrolling cohorts.

Cohort A: 30 patients with relapsed/refractory follicular lymphoma

Cohort B: 30 patients follicular lymphoma, marginal zone lymphoma or SLL

[figure not shown]
4. 3 Treatment Schedule

Lenalidomide capsules will be taken orally daily each day on days 2 - 22, followed by 6 days of no therapy of each 28-day cycle. Obinutuzumab will be given by intravenous infusion on day 1,,2, 8, 15, and 22 of cycle one and on day 1 of each subsequent cycle up to 6 cycles. Patients who do not progress following 6 cycles and are deriving benefit from the combination in the opinion of the treating physician can receive further cycles of combination up to 12 cycles of lenalidomide therapy. (As long as the patient does not exhibit progression, the decision of how many cycles of combination therapy beyond 6 is at the discretion of the treating team and investigator).

Extended dosing of obinutuzumab will begin after combination therapy if patients demonstrate at least stable disease on response assessment. In the extended dosing schedule, obinutuzumab will be administered every 2 months, and in the absence of progression, will be dosed for maximum of 30 months (combination + maintenance).

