5.2.1 Lenalidomide Dose and Schedule

Phase I: In the phase I portion of the study the planned dose of lenalidomide for patients with follicular lymphoma and marginal zone lymphoma (SLL patients not included in phase I portion of study) will be based upon the dose escalation table. (table 1) Patients will receive an oral dose daily on days 2 – 22 followed by 6 days rest (28 day cycle).

Table 3. Dose levels to be tested in phase I portion		
Dose Level	Lenalidomide Dose (days 2-22 followed by 6 days of no therapy)	Obinutuzumab dose
-1	5 mg	1000mg IV
1	10 mg	
2	15 mg	
3	20 mg	

Phase II: Lenalidomide will be administered orally at the maximum tolerated dose (MTD) (as defined by the Phase I portion of the study) on days 2 to 22 of a 28 day cycle in patients with follicular lymphoma and marginal zone lymphoma. Patients with a diagnosis of small lymphocytic lymphoma (SLL) will begin cycle #1 at a maximum dose of 10 mg total daily on days 2 to 22 of a 28 day cycle. This dose will be escalated by 5mg with each cycle up to the MTD if no toxicity is encountered. (see dose modification for lenalidomide table). In the absence of progression or toxicity, patients will remain on lenalidomide treatment for a total of 6-12 months/cycles.

Only one cycle of study drug will be supplied to the patient each cycle.

If a dose of lenalidomide is missed, it should be taken as soon as possible on the same day. If it is missed for the entire day, it should not be made up.

Patients who take more than the prescribed dose of lenalidomide should be instructed to seek emergency medical care if needed and contact study staff immediately. Subjects experiencing adverse events may need study treatment modifications. See Tables 6 and 7.

Supplier

Celgene Corporation will supply Revlimid® (lenalidomide) to study participants at no charge through the Revlimid REMS® program. All physicians who prescribe lenalidomide for research subjects enrolled into this trial and all research subjects enrolled into this trial must be registered in and must comply with all requirements of Celgene's Revlimid REMS® program.

Dosage form

Lenalidomide will be supplied as capsules for oral administration. The capsules are available in 2.5 mg, 5mg and 25mg capsule strengths.

Packaging

Lenalidomide will be shipped directly to the patient. Bottles will contain a sufficient number of capsules for one cycle of dosing.

Storage

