6.2 DOSE MODIFICATION: LENALIDOMIDE

Subjects will be evaluated for AEs at each visit with the NCI CTCAE v4.0, see below for full instruction on initiation of a new cycle of therapy and dose modifications during a cycle of therapy.

Table 6, 7 Lenalidomide dose adjustment steps

Table 6: LENALIDOMIDE Dose Adjustment Steps	
Starting Dose	MTD mg daily for 21 days every 28 days
Dose Level -1	MTD -5 mg daily for 21 days every 28 days
Dose Level -2	MTD -10 mg daily for 21 days every 28 days
Dose Level -3	MTD-15 mg daily for 21 days every 28 days

Table 7: LENALIDOMIDE Dose Adjustment Steps in SLL	
Starting Dose	MTD or max of 10 mg daily for 21 days every 28 days
Dose level +1	Starting dose +5 mg daily for 21 days every 28 days
Dose level +2	Starting dose +10mg daily for 21 days every 28 days
Dose level +3	Starting dose +15mg daily for 21 days every 28 days
Dose level -1	Starting dose -5 mg daily for 21 days every 28 days
Dose level -2	Starting dose -10 mg daily for 21 days every 28 days
Dose level -3	Starting dose -15mg daily for 21 days every 28 days

The minimum dose level is 15mg below MTD or 5mg daily for 21 days, (whichever is higher).

Patients who cannot tolerate or require dose reduction below 5mg daily lenalidomide will not receive further doses of lenalidomide.

If the patient is attaining clinical benefit in the opinion of the treating physician, and has attained at least a partial response, obinutuzumab dosing will continue per study design to a maximum of 21 doses.

The starting dose will be predefined during the phase I portion of the study based upon cohort (see Table 2). In the phase II portion of the study, the starting dose will be the maximum tolerated dose as defined by phase I portion.

6.2.1 INSTRUCTIONS FOR LENALIDOMIDE DOSE MODIFICATIONS OR INTERRUPTION DURING A CYCLE.

Table 8: Dose Modification for Lenalidomide		
NCI CTC Toxicity Grade	Day 2-14 of Cycle	≥Day 15 of Cycle
Grade 3 neutropenia associated with fever (temperature $\geq 38.5^{\circ} \text{C}$) or Grade 4 neutropenia	
 • Hold (interrupt dose). • Follow CBC weekly. • If neutropenia has resolved to \leq grade 2 restart at next lower dose level and continue the cycle until Day 21. 	
 • Omit lenalidomide for remainder of cycle 
If neutropenia is the only toxicity for which a dose reduction is required. G-CSF may be used and the dose maintained for the next cycle at the investigators discretion.

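### The closing text of section 6.2 sets the phase II lenalidomide start at the MTD with no SLL exception; section 5.2.1 caps the SLL start at 10 mg, and Table 7 does not settle which applies

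*Combined protocol and SAP*

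**What the plan says.** Three passages bear directly on the lenalidomide dose at which an SLL patient enters phase II.

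- **Section 6.2, closing text** (after Tables 6 and 7): "In the phase II portion of the study, the starting dose will be the maximum tolerated dose as defined by phase I portion". No histology is singled out, and there is no reference to 5.2.1.
- **Section 5.2.1, phase II paragraph:** the MTD is given to follicular and marginal zone patients. For SLL: "Patients with a diagnosis of small lymphocytic lymphoma (SLL) will begin cycle #1 at a maximum dose of 10 mg total daily", and then "This dose will be escalated by 5mg with each cycle up to the MTD if no toxicity is encountered".
- **Section 6.2, Table 7** (the SLL dose-step table): the starting-dose row reads "MTD or max of 10 mg daily for 21 days every 28 days".

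Section 4.2 adds: "Additional pts will be enrolled into two cohorts at the recommended dose level (MTD) established in Phase I". It then lists "Cohort B: 30 patients follicular lymphoma, marginal zone lymphoma or SLL" without mentioning a separate SLL dose. Sections 2.3.3 and 11.1.2 likewise describe phase II as conducted at the MTD.

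Two other provisions give the point its context. The exclusion criteria in section 3.2 state: "Patients with SLL/CLL will be excluded during the phase I portion of the study". Section 11.1.2 monitors DLT after one cycle within each cohort.

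**The concern.** A reader who takes the dose from the closing text of 6.2 and a reader who takes it from 5.2.1 would give an SLL patient different first doses whenever the MTD exceeds 10 mg. Neither passage says which prevails.

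Two things are at stake. The first is exposure: the MTD will have been set without SLL patients, so their first cycle in phase II is the first time this protocol gives them the combination. The second is interpretation: Cohort B's toxicity rule counts cycle 1 DLTs, and the dose behind that count for SLL patients depends on the passage followed. If practice varied between treating physicians, the count would pool different starting doses.

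**Working it through.** The plan has no figure of its own for this point, so the check compares the passages and then takes a ratio.

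**Inputs**
- Planned lenalidomide levels: 10, 15 and 20 mg (section 2.3.2), with 5 mg as level -1 (Table 1).
- SLL cap in cycle 1: 10 mg, then +5 mg per cycle up to the MTD (section 5.2.1).
- Start under the closing sentence of 6.2: the MTD.

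**Size of the conflict**

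Ratio = MTD / min(MTD, 10 mg). Cycle in which an SLL patient first reaches the MTD under 5.2.1 = (MTD − start)/5 + 1.

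| MTD | First SLL dose, closing sentence of 6.2 | First SLL dose, 5.2.1 (at the cap) | Ratio | Cycle at MTD under 5.2.1 |
|---|---|---|---|---|
| 5 mg | 5 mg | 5 mg | 5/5 = 1.0 | 1 |
| 10 mg | 10 mg | 10 mg | 10/10 = 1.0 | 1 |
| 15 mg | 15 mg | 10 mg | 15/10 = 1.5 | 2 |
| 20 mg | 20 mg | 10 mg | 20/10 = 2.0 | 3 |

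With an MTD of 20 mg, the cycle monitored for DLT is at 10 mg under 5.2.1 and at 20 mg under the closing sentence of 6.2.

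**Does Table 7 decide it?** Its starting-dose row can be read as the lower of the MTD and 10 mg, which agrees with 5.2.1, or as a choice between the two, which does not. The step rows do not settle the matter:

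- From a 10 mg start, the upward rows give 15, 20 and 25 mg, and the downward rows give 5, 0 and −5 mg.
- From a 20 mg start, the upward rows give 25, 30 and 35 mg, and the downward rows give 15, 10 and 5 mg.

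The upward rows suit a 10 mg start better and the downward rows a 20 mg start. The 5 mg floor printed under the table deals with the zero and negative values, but does not say which start was meant.

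**Are the Cohort B operating characteristics affected?** They were recomputed exactly, with independent binomial counts in groups of 10 and stopping at 10 patients (at most 2 responses or at least 7 DLTs) or at 20 patients (at most 6 or at least 11). For a true OR rate of 0.50 and a DLT rate of 0.10:

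- First look: P(X ≤ 2 of 10) = 56/1024 = 0.0547.
- Second look: (120×176 + 210×56 + 252×11 + 210×1)/1024² = 35862/1048576 = 0.0342.
- Sum: 0.0889, as stated. The DLT terms are negligible at a rate of 0.10.

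The other three scenarios tried (DLT/OR of 0.30/0.50, 0.50/0.50 and 0.30/0.30) gave 0.1104, 0.4848 and 0.6574, also as stated. These figures take the DLT rate as given. The contradiction leaves them unchanged, but it leaves unclear which starting dose that rate refers to for SLL patients.

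**The case against.** The strongest reply is that a specific rule qualifies a general one. Section 5.2.1 is the dosing section; it confines the MTD start to follicular and marginal zone patients and sets out a separate SLL schedule. It also sends readers to Tables 6 and 7, and Table 7 exists because SLL is handled differently. On that view the closing sentence of 6.2 merely restates Table 6, and most readers would follow 5.2.1.

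Much of this stands, and it rules out several stronger readings:

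- **That 6.2 starts every phase II patient at the MTD.** The closing sentence is unqualified, but 6.2 contains Table 7 with its own SLL row. The conflict is therefore partly inside 6.2, not simply between sections.
- **That 4.2 is a second, equal contradiction.** It summarises enrolment and does not speak of a starting dose or of cycle 1. It can be read together with titration up to the MTD. It is weaker evidence, although it omits the SLL rule.
- **That all 30 Cohort B patients could be affected.** No histology quota is stated, so 30 is only a ceiling. Phase I patients at the MTD cannot have SLL and count in their relevant cohort. If all six fell in Cohort B, the ceiling would be 30 − 6 = 24.
- **That the stopping rule is miscalibrated.** The documents give no DLT rate by dose and no expected SLL share, so no effect on stopping probabilities can be derived.

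The reply does not remove the contradiction. The 6.2 sentence follows Table 7, speaks of phase II as a whole and carries no exception. Table 7, which should resolve it, is itself ambiguous. The sentence immediately before it points to Table 2 for the phase I starting dose, but Table 2 covers obinutuzumab infusion; the lenalidomide levels are in Tables 1 and 3. That paragraph should not be left to interpretation.

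**Conclusion.** The point holds as an internal inconsistency: the closing sentence of 6.2 is wrong as written or 5.2.1 is, and Table 7 supports either reading. The first SLL dose differs 2-fold between the two rules at an MTD of 20 mg and 1.5-fold at 15 mg. There is no difference at 10 mg or below, so 2-fold is a maximum that requires the top planned level to be the MTD. These ratios take the 5.2.1 start at its 10 mg cap; a lower permitted start would widen them.

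The consequence is limited to the SLL patients' first exposure and to the dose that Cohort B's cycle 1 DLT count describes. That 5.2.1 would probably be followed in practice lowers the likelihood of a discrepancy, but does not cure a dosing statement that would give a different first dose if followed. Nothing here says which starting dose is right.

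**What to change.** Reconcile three places so that they state the same SLL starting-dose rule: the closing sentence of 6.2, the starting-dose row of Table 7 (worded so that it cannot be read both as a minimum and as a choice), and the SLL sentence in 5.2.1. Add a cross-reference to that rule in 4.2. The sponsor decides which rule it is.

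The cost is a clause or a row edit in each place. The reconciliation itself requires no change to the sample size, the stopping boundaries or the analysis.

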Thrombocytopenia \geqGrade 3 (platelet count $< 50,000/\text{mm}^3$)	
 • Hold (interrupt dose). • Follow CBC weekly. • If thrombocytopenia resolves to \leq grade 2 restart at next lower dose level and continue the cycle until Day 21. 	
 • Omit lenalidomide for remainder of cycle
Erythema multiforme \geq Grade 3	
 • Discontinue lenalidomide study drug. 	
 • Discontinue lenalidomide study drug.

2013-0261 - Obinutuzumab Plus Lenalidomide in Low Grade Lymphoma

			Dose
Sinus bradycardia/ other cardiac arrhythmia Grade 2	
 Hold (interrupt) dose. Follow at least weekly. If the toxicity resolves to ≤ grade 1 prior to Day 21 restart at next lower dose level and continue the cycle until Day 21. 	
 Omit lenalidomide for the remainder of the cycle. 	
≥ Grade 3	
 Discontinue lenalidomide study drug. 	
 Discontinue lenalidomide study drug. 	
Allergic reaction or hypersensitivity Grade 2-3	
 Hold (interrupt) dose. Follow at least weekly. If the toxicity resolves to ≤ grade 1 prior to Day 21 restart at next lower dose level and continue the cycle until Day 21. 	
 Omit lenalidomide for the remainder of the cycle. 	
Grade 4	
 Discontinue lenalidomide study drug. 	
 Discontinue lenalidomide study drug 	
Venous thrombosis/embolism ≥ Grade 3	
 Hold (interrupt) dose and start anticoagulation; restart at investigator's discretion (maintain dose level). 	
 Omit lenalidomide for remainder of cycle. Anticoagulation measures as described in Concomitant therapy section below. 	
other non-hematologic toxicity assessed as Lenalidomide-related ≥ Grade 3	
 Hold (interrupt) dose. Follow at least weekly. If the toxicity resolves to ≤ grade 2 prior to Day 21 restart at next lower dose level and continue the cycle until Day 21. 	
 Omit lenalidomide for remainder of cycle. Initiate appropriate supportive care, restart lenalidomide next cycle (decrease by one dose level) 	

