Hyperthyroidism or hypothyroidism	
 Omit lenalidomide for remainder of cycle. evaluate etiology, and initiate appropriate therapy. Restart lenalidomide next cycle (decrease dose by one dose level). 	
 Omit lenalidomide for remainder of cycle evaluate etiology, and initiate appropriate therapy. Restart lenalidomide next cycle (decrease dose by one dose level). 	

adjustments/intervention: lenalidomide associated rash:

Grade

1-2

Day 2-14 of Cycle

- Start supportive

Day ≥ 15 of Cycle

- Start supportive

2013-0261 - Obinutuzumab Plus Lenalidomide in Low Grade Lymphoma

	measures if grade 2	measures if grade 2
Non-blistering rash	
• No dose adjustment• Hold (interrupt) dose.• Startsupportive measures.• Evaluate weekly• If rash resolves to ≤ grade 1 prior to day 21 restart at dose level -1 and continue to Day 21.• Restart next cycle at dose level -1.	
• No dose adjustment• Omit lenalidomide for remainder of cycle.• Startsupportive measures.• Evaluate weekly until rash ≤ grade 1.• Restart next cycle at dose level -1.
Grade 3		
Grade 4*	
• Discontinue lenalidomide• Dermatology evaluation• Startsupportive measures	
• Discontinue lenalidomide• Dermatology evaluation• Startsupportive measures
Desquamating(blistering) rash	
• Discontinue lenalidomide	
• Discontinue lenalidomide
Any Grade*	
• Dermatology evaluation• Startsupportive measures	
• Dermatology evaluation• Startsupportive measures

Suggested supportive measures :

1. Initiate daily oral antihistamines

Examples

- Loratadine 10mg PO daily
- Cetirizine 10mg PO daily
- Diphenhydramine 25mg PO daily

2. Short-course low-dose oral steroids

Example

- Prednisone 10mg PO x 3 days
- Hydrocortisone 20mg PO QAM, 10mg PO QPM x 3 days

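### The grade 3 rash rule restarts lenalidomide at a fixed dose label, so a patient already dose-reduced gets no reduction or, in one case, a higher dose

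*Combined protocol and SAP*

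**What the plan says.** Section 6.2 sets the lenalidomide dose ladder. For patients without SLL, Table 6 starts at the MTD and defines Dose Level -1 as "MTD -5 mg daily for 21 days every 28 days" and Dose Level -2 as "MTD -10 mg daily for 21 days every 28 days". The lowest permitted dose is the higher of MTD minus 15 mg and 5 mg. Below that, "Patients who cannot tolerate or require dose reduction below 5mg daily lenalidomide will not receive further doses of lenalidomide".

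The rash table in Section 6.2.1 handles grade 3 non-blistering rash in two columns:

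- **Onset on Days 2-14.** Hold the drug. If the rash resolves to grade 1 or less before Day 21, "restart at dose level -1 and continue to Day 21". For the following cycle, "Restart next cycle at dose level -1".
- **Onset on Day 15 or later.** Omit the rest of the cycle, then apply the same next-cycle instruction.

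The other rules in Section 6.2.1 that reduce and restart are worded relative to the current dose. Several of the Day 2-14 rules in Table 8 say "restart at next lower dose level and continue the cycle until Day 21". The row for other non-hematologic toxicity (Day 15 or later) and the thyroid row both ask for a decrease of one level at the next cycle.

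**The concern.** The rash row names a position on the ladder, whereas its neighbours name a step. For a first event at the starting dose the two come to the same thing. For a patient already at level -1, whether the earlier reduction was for rash or for another toxicity such as a cytopenia, the row gives no reduction. For a patient at level -2 with an MTD of 20 mg, it gives an increase.

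Followed as written, a patient with a second grade 3 drug rash would be re-exposed at the dose on which it occurred, and a twice-reduced patient could be re-exposed above it. Safety of the combination is a Phase II primary objective (Section 2.2.1), so the dosing rules should not rely on staff departing from a label that the protocol itself defines.

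**Working it through.** The plan states no figure on this point, so the check enumerates the dosing rules.

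**Inputs**

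- Phase II starting dose without SLL: the MTD (Section 6.2).
- Planned dose levels: 10, 15 and 20 mg, with 5 mg as the de-escalation level (Section 4.1, Table 1).
- Ladder: level -k = MTD - 5k mg, not below the larger of MTD - 15 mg and 5 mg (Section 6.2, Table 6).
- Dosing days: 2 to 22 of a 28-day cycle (Section 4.3).

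**Step 1: restart dose after grade 3 non-blistering rash, patients without SLL in Phase II**

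Literal restart = MTD - 5 mg. One-level step = current dose - 5 mg.

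| MTD (mg) | Dose at rash (mg) | Literal restart (mg) | One-level step (mg) | Literal change (mg) | Literal / one-level |
|---|---|---|---|---|---|
| 20 | 20 | 15 | 15 | -5 | 1 |
| 20 | 15 | 15 | 10 | 0 | 15/10 = 1.5 |
| 20 | 10 | 15 | 5 | +5 (5/10 = 50%) | 15/5 = 3 |
| 15 | 15 | 10 | 10 | -5 | 1 |
| 15 | 10 | 10 | 5 | 0 | 10/5 = 2 |
| 10 | 10 | 5 | 5 | -5 | 1 |

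Patients already on 5 mg are left out, because the stop rule in Section 6.2 arguably takes them off lenalidomide. Counting them among the possible reduced doses, the literal rule goes wrong at 2 of 3 for MTD 20 mg (15 and 10, out of 15, 10 and 5), at 1 of 2 for MTD 15 mg (10, out of 10 and 5) and at 0 of 1 for MTD 10 mg. An MTD of 5 mg leaves no reduced dose. Only one case is a rise.

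**Step 2: does Section 6.2.2 repair it?**

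That section requires a one-level reduction at the new cycle if more than 15 days of lenalidomide were omitted, or if the new cycle is delayed by more than 7 days. Take a rash starting on Day d with no restart within the cycle:

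- Omitted dosing days = 22 - d + 1 = 23 - d. This exceeds 15 only if d is 7 or less (d = 7 gives 16; d = 8 gives 15).
- If calendar days are meant, 28 - d + 1 = 29 - d, which exceeds 15 only if d is 13 or less.
- For onset on Day 15 or later, at most 23 - 15 = 8 dosing days or 29 - 15 = 14 calendar days are omitted, so the omission trigger cannot be met. Only the delay trigger could then apply.

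Neither trigger governs a restart within the same cycle. Where one is met, it contradicts the rash row: at 10 mg with an MTD of 20 mg, Section 6.2.2 gives 5 mg and the rash row gives 15 mg.

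**Step 3: other text that might control the dose**

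- The ban on raising a patient's dose is in Section 4.1, for Phase I only.
- Section 6.1.6 lets the physician hold either drug and decide when to resume, and sends redosing to Section 6.2.2. It sets no dose.
- Table 8's row for other non-hematologic toxicity is relative, but it covers toxicities without a rule of their own.

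**The case against.** The strongest reply is that the label was meant as one step down and that most physicians would read it so. Section 6.2.2 supports this: where lenalidomide was halted and restarted one level lower within a cycle, that lower dose carries into the next cycle. The only Phase II escalation the protocol describes is for SLL patients who have had no toxicity, so a dose rise after a grade 3 rash is unlikely to have been intended. The label also has other definitions: a fixed 5 mg in Tables 1 and 3, and the starting dose minus 5 mg in Table 7. Under the 5 mg definition no dose would rise.

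The point about intent is fair, and it is probably what the authors meant. It does not settle the rule. The carry-forward sentence operates only once a one-level reduction has been made and does not say what the rash restart dose is. Tables 1 and 3 are captioned for Phase I and Table 7 covers SLL only, which leaves Table 6 as the definition for these patients.

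The case for low impact also stands in part. Having no reduction requires one earlier reduction; the rise requires two and an MTD of 20 mg. The rash reported with lenalidomide plus rituximab in Section 1.3.1 was grade 1-2. Grade 4 or blistering rash stops the drug, and the investigator may stop treatment at any time. These points limit how often the fault would matter. None of them corrects the dose in the row.

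**Conclusion.** The concern holds: the grade 3 non-blistering rash row is wrong as written for Phase II patients without SLL who have already been reduced. It gives no reduction at 15 mg (MTD 20 mg) or at 10 mg (MTD 15 mg), and a 5 mg rise at 10 mg (MTD 20 mg). The literal restart dose is 1.5 to 3 times what a one-level step would give.

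This rests on reading the label by Table 6. The MTD is not known from the documents; at 10 mg or below there is no effect. The documents give no rate of grade 3 rash in dose-reduced patients, so the number affected cannot be estimated and is likely small. No efficacy endpoint, sample size or analysis is affected.

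The finding does not extend to patients on 5 mg, to SLL patients escalated above their starting dose (for whom the label gives a larger drop, which errs toward safety) or to Phase I. The change should be made because a stated dosing rule can re-expose a patient at the same or a higher dose after a severe drug rash, and correcting it costs almost nothing.

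**What to change.** In the grade 3 non-blistering rash row of Section 6.2.1, replace the fixed label in all three restart bullets with *one dose level below the dose at onset of the rash*. State that the step is applied once, so that a restart within the cycle and the next cycle use the same reduced dose, and that lenalidomide stops if the step would go below 5 mg. If the larger drop to 5 mg below the starting dose is wanted for escalated SLL patients, say so in that row. Leave the Table 8 rows unchanged.

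The cost is a wording change to one table row. Sample size, visits and analysis stay as they are.
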